## 1. SYNOPSIS

### 1.1. Rationale

Individuals with autoimmune disease (AID) are at higher risk of herpes zoster (HZ) compared to immunocompetent individuals [Gupta, 2006; Khan, 2018; Long, 2013; Smitten, 2007; Yun 2016]. Information on the effectiveness of RZV in AID populations is limited. One study from the Veterans Affairs Healthcare System among individuals diagnosed with inflammatory bowel disease (IBD) showed that the recombinant zoster vaccine (RZV) group, when compared with the unvaccinated group, was associated with decreased risk of HZ infection among both the 50-60 years of age (YOA) (0.00 vs 3.93 per 1000 person years) and the >60 YOA (1.80 vs 4.57 per 1000 person-years) [Khan, 2022]. A study evaluating the overall vaccine effectiveness (VE) of RZV in a subgroup of Medicare enrolled patients aged ≥65 YOA with AID reported a 1- and 2-dose VE of 57.7% (95% CI, 50.9, 63.6) and 68.0% (95% CI, 62.3, 72.8), respectively [Izurieta, 2021].

The current retrospective matched cohort database study will use the OptumTM Clinformatics Data Mart database to provide early real-world evidence of the effectiveness of RZV in patients aged  $\geq$ 50 YOA with AIDs. Section 3 provides further details of this study's rationale and background.

# 1.2. Objectives and outcomes

The primary objective is to estimate the VE of 2 RZV doses in preventing HZ in adults aged  $\geq$ 50 YOA with systemic lupus erythematosus (SLE), multiple sclerosis (MS), rheumatoid arthritis (RA), inflammatory bowel disease (IBD), psoriasis (PsO), or psoriatic arthritis (PsA). The primary and secondary objectives are listed in section 4.2. The primary outcome is HZ (Section 4.2) for all objectives.

Twelve matched cohorts for a 1-dose and 2-dose for each AID condition (SLE, MS, RA, IBD [ulcerative colitis (UC), Crohn's disease (CD)], PsO, and PsA) will be considered. Participants will be followed through OptumTM database from index date + 30 days until the earliest date of the occurrence of HZ, termination of continuous enrolment (period of uninterrupted insurance coverage), date of death (described in detail in the statistical analysis plan [SAP]), receipt of a dose of RZV for unvaccinated participants, receipt of RZV dose 2 for 1-dose cohort, receipt of zoster vaccine live (ZVL), or end of the study period (December 31, 2021). To be eligible for the analysis, participants who are >50 YOA at the index date will be required to have at least 365 days of continuous medical and pharmaceutical coverage (allowing administrative gap of 30 days) immediately before index date and 30 days after index date. The 365 days before the index date is defined as the baseline period. Following matching, propensity scores based on the likelihood of receiving RZV versus no RZV vaccination will be calculated using logistic regression models to balance measured confounders among participants receiving RZV and comparator participants with no prior RZV vaccination. The overall incidence rates of HZ for the 2-dose RZV vaccinated cohort and the matched unvaccinated cohort will be estimated. VE will be calculated from the hazard ratio obtained from Cox regression models. Analyses will be conducted separately in RA, IBD (UC, CD), SLE, MS, PsO, and PsA populations. Section 5 provides further study design details.

# 2. SCHEDULE OF ACTIVITIES (SOA)

Below is a list of data extraction procedures that will be considered for this study.

## List of data extraction procedures

#### **Retrospective data collection**

Define code lists and algorithms to extract variables of interest including AIDs, HZ events.

Identify eligible participants and variables of interest; use of algorithms needed to perform the extraction of the data from the OptumTM database.

Extract participant data from different sources within OptumTM database.

Extracted dataset undergoes: - Quality control and validation - Check for consistency with the required format.

Perform quality control and validation.

Perform specification of analysis dataset including derived variables.

Create analysis dataset.

Perform database freeze of the analysis dataset.

Archive programs and outputs of the analysis dataset.

## 3. RATIONALE AND BACKGROUND

HZ, or shingles, results from the reactivation of varicella zoster virus (VZV) and causes a painful, pruritic rash that usually resolves on its own within 1-2 weeks. HZ affects at least 1 million people in the United States each year. An estimated 32% of persons in the United States will experience HZ during their lifetime [Harpaz, 2008]. Furthermore, over 95% of adults ≥50 YOA are seropositive for VZV and susceptible to HZ [Johnson, 2015].

Individuals with AID are at higher risk of HZ than immunocompetent individuals [Gupta, 2006; Khan, 2018; Long, 2013; Smitten, 2007; Yun, 2016]. The incidence rate of HZ among adults with RA is about double than that among immunocompetent (non-RA) adults [Smitten, 2007; Yun, 2016], and it is higher among adults with IBD (e.g., UC or CD) than those without IBD [Gupta, 2006; Khan, 2018; Long, 2013; Yun, 2016]. The risk of HZ in patients with SLE is also twice as high than in the general population [Kawai, 2017a]. Patients with PsO have a higher HZ risk than the general population [Baumrin, 2019; Chen, 2014; Tsai, 2017].

Systemic therapies also play a major role in the risk of HZ. For example, immunosuppressive therapy renders patients with SLE and MS more susceptible to VZV reactivation [Borba, 2010; Manouchehrinia, 2017]. In a recent systematic literature review, patients with PsO or PsA treated with systemic corticosteroids and combination systemic therapy were reported to have increased HZ risk [Baumrin, 2019]. Patients with PsO and PsA had variable HZ risk, depending on disease severity and type of systematic therapy.

219111 (EPI-ZOSTER-097 VE US DB) Protocol Final

The US Food and Drug Administration (FDA) approved RZV, a 2-dose subunit zoster vaccine containing recombinant glycoprotein E in combination with the novel adjuvant AS01B, in October 2017 for immunocompetent adults aged ≥50 YOA [FDA, 2017] and in July 2021 for adults aged ≥18 YOA who are or will be at increased risk of HZ due to immunodeficiency or immunosuppression caused by known disease or therapy [FDA, 2021]. The FDA approvals were followed by the recommendations of the Advisory Committee on Immunization Practices (ACIP) of RZV for use in immunocompetent adults aged ≥50 YOA [Dooling, 2018] and in immunocompromised adults aged ≥19 YOA [Anderson, 2022].

The GSK 2-dose RZV vaccine demonstrated efficacy in preventing HZ in two phase III randomized controlled trials (RCTs): ZOE-50 and ZOE-70 [Lal, 2015; Dagnew, 2019]. RZV efficacy in these trials was 97.2% (95% CI, 93.7, 99.0) in adults aged ≥50 YOA (ZOE-50) and 91.3% (95% CI, 86.8, 94.5) in adults ≥70 YOA (ZOE-70). Myalgia, injection site pain, and erythema were the most common adverse events (AEs) reported in these trials.

Vaccine efficacy of RZV in immunocompromised adults aged ≥18 YOA was evaluated in a clinical trial that included autologous hematopoietic stem cell transplant (auHSCT) recipients [Bastidas, 2019]. Among auHSCT recipients, RZV efficacy in preventing HZ was 68.2% (95% CI, 55.6, 77.5). Post-hoc vaccine efficacy among adults with hematological malignancies (HM) was 87.2% (95% CI, 44.3, 98.6) [Dagnew, 2019].

Data on RZV effectiveness in AID populations is limited. A recent cohort study evaluated the overall VE of RZV in a subgroup of Medicare enrolled patients aged ≥65 YOA with various immunocompromised (IC) conditions and AIDs and reported overall 1- and 2-dose VE of 57.7% (95% CI, 50.9, 63.6) and 68.0% (95% CI, 62.3, 72.8), respectively [Izurieta, 2021]. Another recent study from the Veterans Affairs Healthcare System among individuals diagnosed with IBD showed that RZV was associated with decreased risk of HZ infection among both the 50-60 years and >60 years of age (YOA) patients [Khan, 2022]. More research is needed to evaluate the effectiveness of RZV in specific AID populations (SLE, MS, RA, IBD, PsO, and PsA).

This study will help to critically inform patient and physician decision-making about vaccinating against HZ in these at-risk populations and support evidence-based AID recommendations and guidelines.

# 3.1. Description of the database

This study will be conducted using data from the health care administrative encounters/claims (United enrollees) of the Clinformatics Data Mart (CDM) OptumTM. CDM OptumTM is a quarterly updated database for members of a large national managed care company affiliated with OptumTM. It includes both commercial and Medicare Advantage health plan enrollees from all 50 states in the United States. The database includes proprietary, deidentified health claims data from a geographically diverse US population (16% West, 20% Midwest, 36% South, and 27% Northeast). In addition to medical claims, pharmacy claims, and outpatient laboratory tests, OptumTM includes data tables related to member inpatient confinements and eligibility data. OptumTM includes

219111 (EPI-ZOSTER-097 VE US DB)
Protocol Final

data with service dates from 2007 to present and approximately 15 – 18 million annually insured lives. The OptumTM database system contains more than 80 million lives, of which more than 40% have more than 4 years of clinical history. Clinical history data are sourced from the electronic health record (EHR) of the large integrated delivery networks (IDNs), with more than 60% of patients having both outpatient and hospital information. Remaining patients come from large multispecialty physician practices. The age and sex distribution of the beneficiaries of OptumTM is similar to that reported by the US Census Bureau for the commercially insured and the Medicare managed care populations. This study will use IDN lives to provide information on healthcare use from both an inpatient and outpatient perspective.

Providers and pharmacies submit administrative claims for payment. These claims are then verified, adjudicated, adjusted, and de-identified prior to inclusion. The deidentified data are fully compliant with the Health Insurance Portability and Accountability Act (HIPAA). Claims for pharmacy services are typically submitted electronically by the pharmacy at the time prescriptions are filled. The claims history is a profile of all outpatient prescription pharmacy services provided and covered by the health plan. Pharmacy claims data include drug name, dosage form, drug strength, fill date, days of supply, financial information, and de-identified patient and prescriber codes, allowing for longitudinal tracking of medication refill patterns and changes in medications. Pharmacy claims are typically added to the research database within 6 weeks of dispensing.

Medical claims or encounter data are collected from all available healthcare sites (e.g., inpatient hospital, outpatient hospital, emergency department, physician's office, surgery center) for virtually all types of provided services, including specialty, preventive, and office-based treatments. Medical claims and coding conform to insurance industry standards. Claims for ambulatory services submitted by individual providers, for example, physicians, use the Health Care Finance Administration 1500 format. Claims for facility services submitted by institutions, for example, hospitals, use the UB-82 or UB-92 format. Medical claims include multiple diagnosis codes recorded with the ICD-10-CM diagnosis codes; procedures recorded with ICD-10-CM procedure codes, Current Procedural Terminology (CPT) codes, or Healthcare Common Procedure Coding System codes; site-of-service codes; provider specialty codes; revenue codes (for facilities); paid amounts; and other information. Typically, facility claims do not include any drugs administered in a hospital.

Specific information in the OptumTM database includes, but is not limited to, the following types of data:

- Enrolment: Beneficiaries are assigned a unique identifier by their insurer, which is linkable to all other data. They may be enrolled multiple times with the same insurer, and the length of each given enrolment "span" may vary substantially.
- Demographic: Includes birth date, sex, race/ethnicity, and ZIP code of the most recently recorded primary residence.
- Pharmacy dispensing: Includes the date of each prescription dispensing, the National Drug Code (NDC).

219111 (EPI-ZOSTER-097 VE US DB)
Protocol Final

- Identifier associated with the dispensed product, the nominal days' supply, and the number of individual units (pills, tables, vials, etc.) dispensed. Over-the-counter medications are not captured in the databases.
- Medical encounter: Includes the healthcare provider, facility of the encounter, admission and discharge dates, encounter type (ambulatory visit, emergency visit, inpatient hospital stay).
- Diagnosis: Includes the date of diagnosis, its associated encounter identifier, admission date, provider identifier, and encounter type, diagnoses with ICD-9-CM and ICD-10-CM codes.
- Procedure: Includes the date of the procedure, its associated encounter identifier, admission date, provider identifier, and encounter type. Procedures are coded as ICD-9-CM and ICD-10-CM Procedure Coding System procedure codes, CPT categories II, III, or IV codes, revenue codes.

### 4. OBJECTIVES AND OUTCOMES

# 4.1. Objectives

This study will assess VE among participants enrolled in the OptumTM database with SLE, MS, RA, IBD (UC, CD), PsO, or PsA who received RZV (vaccinated) compared to participants who did not receive RZV (unvaccinated), as per the objectives described in section 4.2. HZ will define the outcome (Section 4.2) for all objectives in section 4.2.

# 4.2. Study objectives

## **Primary Objectives**

- 1. To estimate VE after 2 doses of RZV for preventing HZ in participants ≥50 YOA with SLE.
- 2. To estimate VE after 2 doses of RZV for preventing HZ in participants ≥50 YOA with MS
- 3. To estimate VE after 2 doses of RZV for preventing HZ in participants ≥50 YOA with RA.
- 4. To estimate VE after 2 doses of RZV for preventing HZ in participants ≥50 YOA with IBD
- 5. To estimate VE after 2 doses of RZV for preventing HZ in participants ≥50 YOA with PsO
- 6. To estimate VE after 2 doses of RZV for preventing HZ in participants ≥50 YOA with PsA

219111 (EPI-ZOSTER-097 VE US DB)
Protocol Final

### **Secondary Objectives**

- 1. To estimate VE after 2 doses of RZV for preventing HZ in participants ≥50 YOA with IBD stratified by condition (UC, CD)
- 2. To estimate VE after 2 doses of RZV for preventing HZ in participants ≥50 YOA with either PsO or PsA.
- 3. To estimate VE after 2 doses of RZV for preventing HZ in participants ≥50 YOA with SLE stratified by age, gender, time since vaccination, time interval between two doses, and medication category (mutually exclusive) based on current use at the index date.
- 4. To estimate VE after 2 doses of RZV for preventing HZ in participants ≥50 YOA with MS stratified by age, gender, time since vaccination, time interval between two doses, and medication category (mutually exclusive) based on current use at the index date.
- 5. To estimate VE after 2 doses of RZV for preventing HZ in participants ≥50 YOA with RA stratified by age, gender, time since vaccination, time interval between two doses, and medication category (mutually exclusive) based on current use at the index date.
- 6. To estimate VE after 2 doses of RZV for preventing HZ in participants ≥50 YOA with IBD stratified by condition (UC, CD), age, gender, time since vaccination, time interval between two doses, and medication category (mutually exclusive) based on current use at the index date.
- 7. To estimate VE after 2 doses of RZV for preventing HZ in participants ≥50 YOA with PsO stratified by age, gender, time since vaccination, time interval between two doses, and medication category (mutually exclusive) based on current use at the index date.
- 8. To estimate VE after 2 doses of RZV for preventing HZ in participants ≥50 YOA with PsA stratified by age, gender, time since vaccination, time interval between two doses, and medication category (mutually exclusive) based on current use at the index date.
- 9. To estimate VE after 2 doses of RZV for preventing HZ in participants ≥50 YOA with either PsO or PsA stratified by age, gender, time since vaccination, time interval between two doses, and medication category (mutually exclusive) based on current use at the index date.
- 10. To estimate VE after 1 dose of RZV for preventing HZ in participants ≥50 YOA with SLE.
- 11. To estimate VE after 1 dose of RZV for preventing HZ in participants ≥50 YOA with MS.
- 12. To estimate VE after 1 dose of RZV for preventing HZ in participants ≥50 YOA with RA.
- 13. To estimate VE after 1 dose of RZV for preventing HZ in participants ≥50 YOA with IBD stratified by condition (UC and CD).

219111 (EPI-ZOSTER-097 VE US DB)
Protocol Final

- 14. To estimate VE after 1 dose of RZV for preventing HZ in participants ≥50 YOA with PsO.
- 15. To estimate VE after 1 dose of RZV for preventing HZ in participants ≥50 YOA with PsA.
- 16. To estimate VE after 1 dose of RZV for preventing HZ in participants ≥50 YOA with either PsO or PsA.
- 17. To estimate overall VE after 2 doses of RZV for preventing HZ in participants ≥50 YOA with selected AIDs.

### 4.3. Outcomes

The primary outcome is the HZ event which can be identified with a high PPV > 80% based on diagnosis codes, with additional accuracy established through the requirement for use of an antiviral medication if only one outpatient claim is considered [Zhang, 2012]. A recent study has shown a high PPV of 97.5% for an ICD-10 code for HZ accompanied by either a prescription or laboratory test results [Baxter, 2018]. An HZ event will be defined by the occurrence of either:

- At least 1 inpatient claim with a HZ diagnosis (identified by pre-defined ICD-10 codes); OR
- At least 2 outpatient claims with HZ diagnosis which are no more than 30 days apart:
   OR
- At least 1 outpatient claim with HZ diagnosis with a pharmacy claim for anti-viral treatment within 7 days before or after the claim with HZ diagnosis.

HZ diagnosis codes and medications are shown in Appendix 4.

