# 5.2 Limitations and strengths

#### 5.2.1 Limitations

Various limitations must be considered in a retrospective matched cohort study design, including confounding, bias, and misclassification.

1. Definition of the cohorts: Though the majority of the algorithms that will be used to identify participants with AIDs have demonstrated a good positive predictive value (PPV) (Section 7.5), some misclassification is expected using the validated AID-specific algorithms given the difficulty in diagnosing some AIDs (e.g., SLE, MS). In addition, some participants with well controlled AIDs may not be captured, with algorithms biasing towards a higher risk group. To improve confidence in the definitions, similar algorithms that are being used in studies that are targeting AID

219111 (EPI-ZOSTER-097 VE US DB)
Protocol Final

populations [EPI-ZOSTER-041; EPI-ZOSTER-044] will be used. These studies rely on specialists (e.g., neurologists, rheumatologists, dermatologists) consultation to provide expert opinion on the definitions of the AIDs.

- 2. Outcome misclassification: Some participants that are reported as having a HZ occurrence may not have an accurate diagnosis of HZ occurrence, which may result in a possible underestimation of VE. However, this is expected to be minimal as the detection of HZ using an ICD-10 diagnosis code for HZ (B02.xx) from hospital, emergency department, or ambulatory visit diagnoses, and dispensing for an oral antiviral (acyclovir, valacyclovir, or famciclovir) within 7 days before or after the HZ diagnosis has been used to evaluate the HZ occurrence based on the available literature [Izurieta, 2021]. Systematic differences in HZ misclassification between vaccinated and unvaccinated are not expected.
- 3. Exposure misclassification: It is possible that some participants who are reportedly unvaccinated may have received RZV prior to entering the dataset, leading to an underestimation of VE. Receipt of RZV dose 1 or 2 will be identified from administrative and claims data by means of Current Procedural Terminology (CPT) code 90750 and National Drug Code (NDC) codes 58160-828-01, 58160-829-01, 58160-819-12, 58160-828-03, 58160-829-03, and 58160-823-11 to minimize the risk of exposure misclassification. Additional codes for identification of RZV vaccination may be considered if relevant codes become available in the future.

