#### 7.3. Exclusion criteria

Participants will be excluded from the study if the following exclusion criteria are met:

- Any previous RZV doses before index date (for unvaccinated participants only) using all available data.
- Receipt of second dose of RZV less than 28 days apart since ACIP guidelines state that these participants must repeat the second dose [Dooling, 2018].
- Receipt of ZVL any time during the baseline as this may affect rates of HZ.
- HZ diagnosis or prescription fills for oral acyclovir, valacyclovir or famciclovir
  given specifically for HZ and within 30 days of index date since it is unclear if the
  HZ episode began before or after the index date and whether the length of time since
  vaccination (for RZV vaccinated participants) is long enough to allow for sufficient
  development of immunity.
- HZ diagnosis or prescription fills for oral acyclovir, valacyclovir or famciclovir in the 12 months before the index date to ensure that HZ diagnoses after the index date are new, rather than carried over from HZ episodes prior to the index date.
- Postherpetic neuralgia (PHN) diagnosis in the 12 months before the index date.
- Censoring events within 30 days after the index date (before the start of follow-up) (Section 7.7).
- Follow up time is less than 3 months after the follow up start date.

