### 13.4.2. Codes and medications for the diagnosis of herpes zoster

	Diagnosis code or medication generic names	
Codes/medications for herpes zoster diagnosis		
Herpes Zoster	B02.xx	
Medications to treat herpes zoster	Acyclovir, valacyclovir, or famciclovir	

Codes will be updated as needed if additional codes are identified.

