# 13.4.5. NDC Codes Used to identify herpes zoster antivirals

rug	NDCs
	00093363020, 00093894001, 00093894005, 00093894019, 00093894093, 00093894301, 00093894305, 00093894319, 00093894393, 00093894701, 00093894705, 00093894719, 00093894793,
	00168082515, 00168082530, 00172426660, 00172426670, 00172426760, 00172426770, 00172426860, 00172426870, 00182266600, 00182266689, 00182266700, 00182266789, 00182820000,
	00182820089, 00228260511, 00228260550, 00228260611, 00228260650, 00228260711, 00228260750, 00364269201, 00378025301, 00378025305, 00378030201, 00378146801, 00378220001,
	00378220005, 00378870006, 00378870049, 00378871273, 00395809719, 00395809762, 00440103030, 00440103130, 00440603001, 00440603005, 00440603030, 00440603060, 00440603081,
	00440603101, 00440603105, 00440603125, 00440603130, 00440603181, 00440603301, 00440603305, 00440603310, 00440603320, 00440603381, 00440703005, 00440703025, 00440703030,
	00440703050, 00440703060, 00440703081, 00440703083, 00440703085, 00440703089, 00440703125, 00440703130, 00440703181, 00440703185, 00440703189, 00440703310, 00440703320,
	00440703350, 00440703381, 00440703385, 00440703389, 00472008216, 00591033501, 00591033505, 00591033601, 00591033605, 00591115930, 00591269201, 00591269205, 00713063015,
	00713063031, 00904578961, 00904579061, 00904579961, 00904612161, 10544002640, 10544002725, 10544003925, 10544003940, 10544010125, 10544010225, 10544010240, 10544010340,
	10544014625, 10544014630, 10544015124, 10544015130, 10544015160, 10544020435, 10544020440, 10544020450, 10544094214, 10544094260, 12634069771, 13411018201, 13411018203,
	13411018206, 13411018209, 13411018210, 13411018301, 13411018303, 13411018306, 13411018309, 13411018310, 13668051501, 13668051502, 15455950001, 15455950002, 15455950003,
	15455950005, 15455950008, 15455950009, 1659000325, 16590000330, 16590000335, 16590000350, 16590000360, 16590037020, 16590037030, 16590037040, 16590037090, 16714066801,
	16714066802, 16714088501, 16714088502, 17236085301, 17236085401, 17856008205, 21695000925, 21695000930, 21695001015, 21695001020, 21695001021, 21695001025, 21695001030,
	21695001060, 21695001090, 21695001121, 21695001125, 21695001130, 21695001135, 21695001140, 23155014601, 23155022701, 23155022705, 23155022801, 23155022805, 23155022901,
	23155022905, 23490501101, 23490501201, 23490501202, 23490501203, 23490501204, 23490501301, 23490501302, 23490501303, 23490501304, 23490501501, 23490501501, 23490501502, 23490501503,

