## 219111 (EPI-ZOSTER-097 VE US DB) Protocol Final

Drug	NDCs
Acyclovir Susp 200 Mg/5Ml	50962045360, 60346085434, 60346085471
Acyclovir, Micronized	28595059277
Acyclovir/ Hydrocortis one	00037050105, 00187510401
Acyclovir/ Lidocaine Hcl	28595097362
Famciclovir	00054019613, 00054019713, 00054019813, 00093811756, 00093811856, 00093811956, 00378449093, 00378449193, 00378449293, 00440750002, 00440750010, 00440750121, 00440750160, 00440750202, 00440753121, 00591327130, 00591327230, 00591327330, 00781562031, 00781562131, 00781562231, 16714030001, 16714030401, 16714030501, 16714061401, 16714061501, 16714061601, 31722070630, 31722070730, 31722070830, 33342002407, 33342002507, 33342002607, 42291027530, 42291027530, 42291027730, 50090306600, 50090333700, 50268030511, 50268030513, 50268030613, 50268030613, 50268030711, 50268030713, 52959094604, 52959094621, 54569604600, 54569604601, 54868590500, 54868590501, 54868590503, 54868590504, 55289016803, 59762270001, 59762270301, 60429035930, 60429036030, 60429036130, 60505324503, 60505324603, 60505324703, 60687010325, 60687010395, 63187091921, 63187099821, 63187099821, 63187099821, 63187099830, 65862046530, 65862046630, 65862046730, 69097026902, 69097027202, 00078036615, 00078036615, 00078036815, 00078036861, 00078036864, 00440752802, 49999030821, 49999030830, 54348062310, 54569453300, 54569453400, 54569453401, 54569466000, 54868388200, 54868388201, 54868396900, 54868396901, 54868400900, 54868400901, 68115040730, 68115040760, 68115040830, 68115040860, 68115040801, 68115040921, 68115040930, 68115040960

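### One route to the primary HZ outcome accepts an antiviral claim of any route, while the protocol's defence of the outcome and its antiviral exclusions refer to oral antivirals only

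*Protocol*

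**What the plan says.** - **Outcome, section 4.3.** An HZ event can be established in three ways: an inpatient claim, two outpatient claims no more than 30 days apart, or one outpatient claim confirmed by a drug. In the third, a single outpatient HZ code is enough if it comes "with a pharmacy claim for anti-viral treatment within 7 days before or after the claim with HZ diagnosis". The section adds that "HZ diagnosis codes and medications are shown in Appendix 4".
- **Drug names, section 13.4.2.** The medications are "Acyclovir, valacyclovir, or famciclovir", with no route.
- **Code list, section 13.4.5.** Under the title "NDC Codes Used to identify herpes zoster antivirals", the list gives plain acyclovir, acyclovir sodium, famciclovir, valacyclovir and some combination products. Among these are acyclovir/hydrocortisone (two codes) and "Acyclovir/ Lidocaine Hcl" (one code). No route column or route filter is shown.
- **Defence of the outcome, section 5.2.1, item 2.** Misclassification is expected to be minimal because HZ is detected by a B02 code and "dispensing for an oral antiviral (acyclovir, valacyclovir, or famciclovir") within 7 days either side.
- **Washout, section 7.3.** One criterion excludes an HZ diagnosis or "prescription fills for oral acyclovir, valacyclovir or famciclovir in the 12 months before the index date". The other antiviral criterion, for the 30 days around index, is also limited to oral fills.

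**The concern.** The antiviral condition is there to make a single outpatient code specific; section 4.3 says that it adds accuracy when only one such claim exists. How much it adds depends on which drugs may satisfy it. Followed literally, section 4.3 and the list in 13.4.5 allow a non-oral acyclovir fill to do so. The argument in 5.2.1 therefore supports a narrower outcome than the one a programmer would build.

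The outcome and its washout also use different drug sets. A person whose only antiviral fills in the prior 12 months were non-oral, and who has no HZ or postherpetic neuralgia code, is not excluded by section 7.3. A later non-oral fill can still confirm a single HZ code for the same person.

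The same outcome serves all six primary objectives and every secondary one. Section 5.2.1 itself says that falsely recorded HZ may lead to underestimated VE and that no systematic difference between the groups is expected. Any effect would therefore be toward zero.

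**Working it through.** **1. The texts side by side**

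| Section | Use | Route |
|---|---|---|
| 4.3, third route | Confirms a single outpatient HZ code | None stated |
| 13.4.2 | Generic names for the outcome | None stated |
| 13.4.5 | Codes for HZ antivirals | None stated; includes two acyclovir combinations |
| 5.2.1, item 2 | Argument that misclassification is minimal | Oral |
| 7.3, both antiviral criteria | Exclusion around and before index | Oral |

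The first three rows do not agree with the last two. The update clause in 13.4.2 provides for additional codes; it does not provide for removing any.

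**2. Effect of false events on VE**

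No figure stated in the protocol is disputed here. For scale, Table 2 gives 2781 HZ events in 179,079 person-years for unvaccinated rheumatoid arthritis: 2781 / 179,079 × 1000 = 15.53 per 1000, as stated. This is close to the middle planning rate of 15 in section 11.1.

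Let the true unvaccinated rate be λ, the true hazard ratio HR, and the false-event rate f in both groups (equal because 5.2.1 expects no systematic difference). Let q = f / (λ + f) be the false share of unvaccinated events. Then

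- observed HR = (λ·HR + f) / (λ + f) = (1 − q)·HR + q
- observed VE = (1 − q) × true VE

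The protocol gives no value for q, so the following values are assumptions:

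| q | True VE 70% observed as | True VE 50% observed as |
|---|---|---|
| 0.5% | 0.995 × 70 = 69.65% | 49.75% |
| 1% | 0.990 × 70 = 69.30% | 49.50% |
| 2.5% | 0.975 × 70 = 68.25% | 48.75% |
| 5% | 0.950 × 70 = 66.50% | 47.50% |
| 10% | 0.900 × 70 = 63.00% | 45.00% |

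**3. What these shares would require**

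At λ = 15 per 1000 person-years, f = λ·q / (1 − q):

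- q = 0.5%: 15 × 0.005 / 0.995 = 0.075 per 1000
- q = 2.5%: 15 × 0.025 / 0.975 = 0.385 per 1000

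If Table 2 counted events as in section 4.3, the same shares would be about 14 to 70 of the 2781 rheumatoid arthritis events (0.005 × 2781 = 13.9; 0.025 × 2781 = 69.5), and about 2 to 12 of the 499 psoriatic arthritis events (2.5; 12.5). The two named combinations account for three codes in a list of several pages. On that basis the upper rows of the table are more plausible than the lower ones. The protocol cannot settle the matter, because the plain acyclovir codes carry no route either.

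**The case against.** The strongest answer is that the mechanism is narrow. A false event by this path needs a B02 code, no inpatient HZ claim, no second outpatient HZ claim within 30 days, no oral antiviral fill within 7 days, and a non-oral fill within 7 days. If any other route or drug qualifies, the non-oral fill adds nothing. Section 5.2.1 already gives the oral reading and discloses both misclassification and its direction. This stands, and it is why the point is small.

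Four stronger readings are tempting, and the protocol does not support them.

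- **That non-oral fills strip the antiviral condition of its specificity, for instance in patients with herpes simplex miscoded as HZ.** The HZ code is still required, some patients given only a topical product have true HZ, and the protocol gives no frequency for such miscoding.
- **That all the validity evidence rests on oral drugs.** The two positive predictive value statements in section 4.3 name no route; only the argument in 5.2.1 does.
- **That the list is known to contain many topical products.** Even for the two combinations, topical use is inferred from the partner ingredient.
- **That the section 7.3 criteria must change.** They are already limited to oral fills.

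None of this removes the contradiction: a programmer working from 4.3 and 13.4.5 as written would count the non-oral fills.

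**Conclusion.** The point holds as an inconsistency in the definition of the primary outcome. Section 4.3 with Appendix 4 admits antivirals of any route, while 5.2.1 and 7.3 specify oral ones. The direction of any bias is toward zero VE, assuming similar false-event rates in both groups, as the protocol expects.

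The size is unknown and probably small. At an assumed false share of 0.5% to 2.5% of unvaccinated events, a true VE of 70% loses about 0.35 to 1.75 percentage points, and a true VE of 50% about 0.25 to 1.25. The protocol gives no ground for claiming a material bias in the six primary estimates. Severity: minor.

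**What to change.** 1. In section 4.3, replace the general reference to antiviral treatment with the drug set already used in 5.2.1: oral acyclovir, valacyclovir or famciclovir.
2. Screen the 13.4.5 list by route. For use in the outcome, remove the two combination products and any other non-oral codes that the screening finds.
3. State explicitly whether acyclovir sodium counts. It is listed separately without a route, appears to be an injectable form, and would drop out under a strict oral rule.
4. Leave section 7.3 as it is.

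The cost is a wording change and a code-list edit before programming. The downside is that a few true cases, treated only with a non-oral product and with a single outpatient claim, would be lost. Cases with an inpatient claim, or with two outpatient claims no more than 30 days apart, would still be captured by the other two routes.
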